
2.5 Study Procedures
	
Interventions
 
Common management will include the following
 
 1. Pre-medication other than oral analgesic (such as paracetamol) will not be used. 2. Induction will be with intravenous propofol, including co-induction consisting of fentanyl 0.5-3.0 mcg/kg, or equivalent short acting opiate including remifentanyl. 3. Analgesia will consist of multimodal analgesia as determined by the anesthesiologist to treat the degree of pain, but in principle to avoid long acting opiates, e.g. use intraoperative short acting opiates, 1 g acetaminophen qid, NSAID's including Cox II inhibitors (such as paracoxib 40mg i.v.), or oxycontin 10-20mg 6 hourly. 4. Dual antiemetic therapy as per hospital guidelines 5. The maintenance anesthetic will be desflurane, and will be titrated to effect by the attending anesthesiologist 6. Rocuronium administration: for moderate neuromuscular block an initial dose of 0.6 mg/kg, with repeat doses of 0.15mg/kg given if the TOF >2 twitches. After completion of the majority of surgical resection, the level of block may be reduced to at least 3 twitches in preparation for the end of surgery. 
For DNB, the initial dose will be 1.2 mg/kg and repeat doses of 0.15 mg/kg until PTC ≤ 2. TOF counts may be checked as frequently as every 15 seconds, but the PTC count interval must be at least 2 minutes (26).
 
 7. If vecuronium (a similar steroidal muscle relaxant) is used instead of Rocuronium, then the dose is reduced to 10% of the dose of rocuronium, and titrated to achieve the same TOF endpoints. 8. Reversal of neuromuscular block 
 a. Neostigmine 50 micrograms/kg coupled with atropine 20 micrograms/kg or glycopyrrolate 5 micrograms/kg, to a maximum dose of neostigmine of 5.0 mg. The neostigmine should not be administered until the TOF has at least 3 twitches present. b. Sugammadex dosage will be adjusted to body weight and PTC/TOF count at the time of reversal, and not administered until PTC at least 1. Dosage will be 4mg/kg if TOF = 0 and PTC ≥ 1; and 2 mg/kg if TOF ≥1. 9. Extubation for all groups will occur when the TOF has 4 twitches with no visible fade, (or a TOF ratio > 0.7 for institutions using a TOF ratio measurement device) adequate respiration and degree of alertness as determined by the anesthesiologist 																

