as safe for extubation. Patients should not leave the operation room until TOF has 4 twitches with no visible fade, or for institutions using a TOF ratio measurement device, a TOF ratio > 0.9.

Intervention –groups

1. ModNB - participants will receive moderate neuromuscular blockade with rocuronium aiming for TOF 0-2 twitches, with neostigmine reversal when the TOF at least 3 twitches. After completion of the majority of surgical resection, the level of block may be reduced to at least 3 twitches in preparation for the end of surgery.

2. **DNB**– participants will receive DNB aiming for a post tetanic count of 1-2, which will be maintained until removal of the laparoscopic ports, with reversal using sugammadex.

Study assessments protocol

Quality of recovery will be assessed using the Postoperative Quality of Recovery Scale (PostopQRS) see www.postopqrs.com. The survey takes around 5-6 minutes on each occasion to administer and is conducted either face-to-face whilst the participant is in hospital or via the telephone when discharged. Five recovery domains are assessed (physiological, nociceptive, emotive, function (ADL) and cognitive, and an additional overall patient perspective domain is recorded including satisfaction.

The scale will be conducted prior to surgery (baseline) and at 15 mins, 40 mins, 1 and 3 days, 1 and 2 weeks, 1 and 3 months after surgery to track recovery from the immediate to long-term.

Outcome measurements

Primary outcome

The most sensitive recovery domain of the Postoperative Quality of Recovery Scale to the effects of short acting drugs and avoidance of neostigmine is cognition. The primary outcome will be the cognitive domain at 1 week after surgery, when it is expected that most of the acute inflammation will have resolved, and analgesia requirements minimal.

Secondary outcomes

1. Recovery for all domains and within domains at the other time points of measurement (15 minutes, 40 minutes 1 day, 3 days, 1 and 2 weeks, and 3 months following cessation of anaesthesia). The domains of recovery are physiological, nociceptive, emotive activities of daily living, cognitive and overall patient perspective.

2. Compliance with protocol to ensure deep block or light/moderate block, and correctly assigned anaesthetic.

3. Anaesthesia, surgical (first incision to last stitch), operating room, and PACU times, and hospital length of stay

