	
4. Incidence of persistent neuromuscular block (TOF < 4 twitches or visible fade, or TOF ratio < 0.9) upon arrival in the PACU.
 
5. Surgical operating conditions measured by maximal inflation pressure required for surgery, and number of times that organ movement occurred (due to diaphragmatic movement or abdominal wall tone), and overall surgical satisfaction using a 1-5 Likert scale (1 = very unacceptable, 2 = unacceptable, 3 = acceptable, 4 = good, 5 = excellent).
 
Ethical issues
 
This study will be reviewed by the Melbourne Health HREC. All patients will receive a written plain language statement and will provide informed written consent.
 
Both neuromuscular reversal drugs are commonly used in Australia. If the participating anesthesiologist believes that the anesthetic regimen is inappropriate, then the patient will not be recruited into the study. The concept of deep neuromuscular block is relatively new in laparoscopic surgery as it can only be safely performed if reversal can be reliably achieved in an acceptable time frame. Accordingly, the deep neuromuscular block group will receive sugammadex using dosage guidelines according to body weight and degree of neuromuscular block at the time of reversal. Each PostopQRS measurement takes approximately 5-10 minutes, and is not onerous or stressful to the patient. However, if the patient does not wish to participate further, then they may withdraw from the study. Measurements performed after discharge from hospital are conducted via telephone interviews and do not require the patient to return to the hospital or other location. The interviews are arranged between the researcher and patient at a time of mutual convenience.
																														

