
2.6 Study Duration
	
Anticipated time-line
 
The aim is to recruit an average of 4-6 patients per week (at least 4 hospitals to participate, with potential to add more hospitals). That timeline for the study schedule is listed below, though could advance earlier if recruitment is faster than anticipated.
 
  
 Objective	3 months	3-12 months	12 -21 months	21-24 months	
   
 Ethics	XXXXXXXX				
 
 Recruit 40%		XXXXXXXXXX			
 
 Recruit 100%			XXXXXXXXXX		
 
 Complete 3 month follow up				XXXX	
 
 Analysis and manuscript					
  
	Objective	3 months	3-12 months	12 -21 months	21-24 months	Ethics	XXXXXXXX				Recruit 40%		XXXXXXXXXX			Recruit 100%			XXXXXXXXXX		Complete 3 month follow up				XXXX	Analysis and manuscript				
Objective	3 months	3-12 months	12 -21 months	21-24 months																											
Ethics	XXXXXXXX																														
Recruit 40%		XXXXXXXXXX																													
Recruit 100%			XXXXXXXXXX																												
Complete 3 month follow up				XXXX																											
Analysis and manuscript																															

2.7 Statistical Analysis and Sample Size Justification
	
The team statistician is [name], Statistical Consulting Centre, Department of Mathematics, The University of Melbourne, who will oversee the statistical analysis.
 
Study size
 
Sample size estimates are based on the primary outcome of cognitive recovery at 1 week after surgery, and a clinically important difference in cognitive recovery at 1 week
																														

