	
after surgery of 15%. Estimates of cognitive recovery are based on prior PostopQRS research and using multiple ages and surgical cohorts. It is estimated that the cognitive recovery for this cohort and duration of surgery will be 85% if there is good recovery. Using a two tailed estimate and Chi-squared analysis, alpha of 0.05, and power of 90%, with 1:1 allocation ratio; the sample size required to detect an absolute difference of 15% is 161 per group, which will be rounded up to a total sample size of 350 patients to account for potential non-completion of the study
 
Statistical methods
 
Variables of “recovery” are dichotomized to "recovered" or "not recovered" based on whether they have achieved baseline values or better at each of the time points when measurement is performed. A tolerance factor is included in the scoring of cognitive recovery to allow for performance variability (5). Statistical analysis for the primary outcome will be with the Chi-squared test. For the secondary outcomes of recovery over time, analysis will be performed using the a general linear mixed model to investigate group differences over time. Continuous data will be analyzed using independent samples t test, or RM ANOVA for repeated measurements. A P<0.05 will define statistical significance, and P<0.01 will define statistical significance for secondary endpoints to reduce risk of Type I error. Analysis is intention to treat.
 
Randomization
 
The randomization sequence will be produced using a computer generated randomization sequence, in unequal blocks and stratified for gynecological and abdominal surgery. Concealment will be by placing the card containing the allocation information in double opaque sealed envelopes, and concealment will be maintained until after recruitment and the patients is admitted to the operating theatre. The treating anesthesiologist will then open the envelopes to reveal the allocation. A non-participant in any process of the study will perform preparation of the envelopes. A copy of the randomization sequence will be stored in a separate databank, which is password protected and not available to the investigators until the study is complete.
 
Blinding
 
Due to the nature of the drugs, it is not possible to blind the treating anesthesiologist to the allocation, but the patient and study investigators who collect the PostopQRS data will be blinded to allocation.

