### 3.4. Framework

Two-center double-blind, placebo-controlled, parallel-group, randomized, phase IV study with 1:1 allocation ratio.

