## 6.2. Analysis Methods

A Fisher's Exact test was used to analyze the primary outcome of cognitive recovery at week 1 following laparoscopic surgery. A Generalized Linear Mixed Model (GLMM) test was used to analyze the recovery within and across all domains over time, including patient satisfaction. For the secondary outcomes, GLMM was used for analysis of the recovery domains and a T test was used for continuous data.

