## 6.4. Additional Analyses

No additional analysis was conducted. All analyses have been previously mentioned.

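### Does counting residual block by either a visible-fade check or a TOF ratio make secondary outcome 4 uninterpretable?

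*Protocol*

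**What the plan says.** The outcome is "Incidence of persistent neuromuscular block (TOF < 4 twitches or visible fade, or TOF ratio < 0.9) upon arrival in the PACU", worded alike in Protocol 2.5 (Outcome measurements) and SAP 6.1.

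Two rules in Protocol 2.5 (Study Procedures, item 9) pair the same bedside sign with different ratios:

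- At extubation: "Extubation for all groups will occur when the TOF has 4 twitches with no visible fade, (or a TOF ratio > 0.7" where the institution has a ratio device).
- Before leaving the operating room: four twitches without visible fade, "or for institutions using a TOF ratio measurement device, a TOF ratio > 0.9".

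Randomization is "in unequal blocks and stratified for gynecological and abdominal surgery" (Protocol 2.7; SAP 3.2), so neither site nor monitor is a stratum. The SAP describes a "Two-center double-blind, placebo-controlled, parallel-group, randomized, phase IV study with 1:1 allocation ratio" (3.4), whereas Protocol 2.6 expected "at least 4 hospitals to participate, with potential to add more hospitals".

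SAP 6.2 gives Fisher's exact test for the primary outcome. For secondary outcomes, "GLMM was used for analysis of the recovery domains and a T test was used for continuous data". SAP 6.4 then states: "No additional analysis was conducted. All analyses have been previously mentioned". Secondary outcomes are judged at P<0.01 (SAP 4.2), with 95% confidence intervals (SAP 4.3).

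**The concern.** The definition joins two measurements with an *or*, and the documents offer no evidence that they agree. If fade can be absent by eye while the ratio lies between 0.7 and 0.9, the same patient counts or does not count depending on the equipment. With few centers, equipment may coincide with site.

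The exit rule adds to this. A device site should hold a patient at 0.8 in the operating room. A fade-only site may let that patient go, and a fade check in the PACU would then score no event. Such patients would go largely uncounted at both kinds of site.

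Protocol 2.2 expects less residual block after sugammadex than after neostigmine, so uncounted events would fall mainly in the moderate-block arm and shrink the contrast. At stake is the meaning of one secondary incidence and the power to compare it. The absence of a named test for a binary secondary outcome looks like a second hole in the same place.

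**Working it through.** **1. The plan's own figure.** The only design calculation is for the primary outcome (Protocol 2.7): 85% versus 70%, two-sided alpha 0.05, power 90%. With a pooled-variance chi-squared formula and mean rate 0.775:

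n = [1.960 × √(2 × 0.775 × 0.225) + 1.282 × √(0.85 × 0.15 + 0.70 × 0.30)]² / 0.15² = 160.8, so 161 per group.

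This agrees with the plan and has no bearing on outcome 4, for which no rate or power is stated.

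**2. Do the two rules contradict each other?**

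| Moment | Without a device | With a device |
|---|---|---|
| Extubation | 4 twitches, no visible fade | ratio > 0.7 |
| Leaving the operating room | 4 twitches, no visible fade | ratio > 0.9 |
| PACU arrival, non-event | 4 twitches, no visible fade | ratio not below 0.9 |

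The first two rows govern different moments. A device site can apply two thresholds in sequence; a fade-only site has one sign for both. If absence of visible fade implied a ratio above 0.9, it would also satisfy the 0.7 rule. The rows can therefore hold together, and the last two rows agree. What is missing is a statement of how the sign and the ratio relate. That is for the sponsor to clarify; this review proposes no threshold.

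**3. How large could the effect be?** The documents give no residual-block rate and no device share, so the following inputs are assumptions: 175 per arm (350/2); a share *w* of patients at fade-only sites; and, among those patients, a rate in the 0.7-0.9 band without visible fade of 20% (moderate) versus 2% (deep).

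Uncounted events per arm = 175 × *w* × band rate. Power is for an exact two-sided Fisher test at 0.01, had those patients been read by ratio and had there been no other events.

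| *w* | Uncounted, moderate vs deep | Power |
|---|---|---|
| 0.25 | 8.75 vs 0.88 | 38% |
| 0.50 | 17.5 vs 1.75 | 89% |
| 0.75 | 26.25 vs 2.63 | 99% |

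With 10% versus 1% in the band, power runs from 5% to 70% over the same shares; with 30% versus 2%, from 79% to above 99.9%.

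**4. How far do the assumptions drive this?** Take *w* = 0.5 and ratios spread evenly over the band. If fade is invisible only above a ratio *c*, uncounted moderate-arm events are 17.5 × (0.90 − *c*)/0.20:

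- *c* = 0.70: 17.5
- *c* = 0.80: 8.75
- *c* = 0.90: 0

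The table in step 3 also sets all other events to zero. Suppose instead that other, countable events were 10% versus 1% of each arm (also an assumption). Power is then already 89% without the band. Adding the band (a further 10% versus 1% of each arm, so 20% versus 2%) takes it above 99.9%, a gain of about 11 points.

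**5. Is there bias between arms?** Device share is balanced in expectation. With half the patients on each method, the 95% range for a chance difference in share is ±1.96 × √(2 × 0.5 × 0.5/175) = ±0.105. For band rates of 5% to 30%, equal in both arms, that gives a spurious difference of 0.105 × 0.05 to 0.105 × 0.30, or about 0.5 to 3 points in either direction. This is chance variation that a test accounts for, and the exit rule would make it smaller, since few device-site patients should arrive in the band.

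**6. Would a change help?** SAP 3.1 and 3.6 describe a trial already conducted and analyzed. A single PACU method would need a ratio device in every PACU and would now come too late. Stratifying by method recovers no uncounted event: a fade-only stratum read by fade still misses them. The 93% power for 88 per arm at 20% versus 2% applies only if that stratum had been read by ratio.

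**The case for a change.** The strongest case for acting is that the gap is real and cheap to address. The documents provide for two kinds of institution, do not show the two readings to be equivalent, and never say which is used in the PACU. The arms are expected to differ on this outcome, so lost events would weaken a contrast that the trial chose to report. SAP 6.2 and 6.4 together leave this binary outcome without a test, whatever fade does or does not detect. Tabulating by method would cost little.

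Much of this stands as description. The definition is loose, the method is unspecified, and a fade check may not exclude a ratio below 0.9. It does not stand as a reason to alter the plan. No passage says that fade is invisible between 0.7 and 0.9, and none says that both kinds of site took part; the two centers in SAP 3.4 may have used the same monitor. The missing test is a gap that an analyst fills without difficulty: SAP 6.2 already uses Fisher's exact test for a binary outcome, and SAP 4.2 and 4.3 supply the significance level and the interval. A breakdown by method belongs in the report of results, labelled post hoc if made after allocation was known.

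**Conclusion.** The concern describes a true looseness in one secondary outcome but does not call for a change. The two bedside rules are not in stated contradiction, the arms remain comparable on average, and an observed arm difference stays informative. The possible loss runs from no events to 26.25 versus 2.63 of 175 per arm at band rates of 20% versus 2%, and would be larger at higher rates. Every figure in that range rests on assumed rates and device shares. None of the remedies would recover an event or correct a bias at this stage. The primary outcome and its 161 per group are unaffected. A reader of the results should learn which PACU reading was used and that a fade check may not exclude a ratio below 0.9; that is a matter of reporting.

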user-defined intervals. From some of the subsequent discriminant validation studies, time points have included early and late measures such as 15 minutes, 40 minutes, 1 and 3 days, and 3 months after the completion of anesthesia (typically defined as after the last surgical stimulation). Recovery is broadly defined as return to baseline values or better, except for the cognitive domain where a tolerance factor is included to allow for normal performance variability, such that patients are allowed to perform a little worse than baseline as still be scored as recovered (5). Because repeated tests tend to have a learning effect, the cognitive domain uses parallel forms, and only a small learning has been shown (5).

One of the most important benefits of the PostopQRS scale is that it enables recovery to be quantified and measured. This makes it possible to compare different interventions with the express purpose of developing clinical interventions to improve quality of recovery. The PostopQRS offers a tool to provide the recovery process to be examined. There are no other tools in existence that provide a comprehensive, sensitive assessment of the multiple aspects or domains of recovery, and is yet relatively simple to perform. Validation studies have been performed and show good discriminative ability (5-8). Ease of use is facilitated by using a web-based data entry system and the ability to use the telephone to conduct surveys after discharge from hospital. Telephone survey has been shown to be equivalent to face to face interviews using the PostopQRS (5). Further, the PostopQRS allows users to drill down to identify which recovery domain is affected for individuals in real time as well as for group audit.

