#### 5.5. Baseline Patient Characteristics

The following characteristics was summarized in a table format as either Mean  $\pm$  SD (continuous data) on (%) (discrete data): Age, Gender, ASA status, Obesity, Education, Alcoholic consumption, Smoking status, Pre-existing conditions, Problems with previous anesthesia, Employment Status..

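### The patient's own pre-operative cognitive result sets the pass mark for the primary endpoint, but the SAP neither tabulates it by arm nor uses it in the primary analysis.

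*Protocol*

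**What the plan says.** Protocol 2.5 fixes the endpoint: "The primary outcome will be the cognitive domain at 1 week after surgery". It describes one pre-operative administration: "The scale will be conducted prior to surgery (baseline) and at 15 mins", followed by the later time points. Protocol 2.7 (Statistical methods) dichotomizes recovery "based on whether they have achieved baseline values or better at each of the time points when measurement is performed" and adds a tolerance for cognition. SAP 2.1 explains its effect: "patients are allowed to perform a little worse than baseline as still be scored as recovered". Neither document gives the size of the tolerance.

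SAP 5.5 lists the baseline characteristics to be summarized: "Age, Gender, ASA status, Obesity, Education, Alcoholic consumption, Smoking status, Pre-existing conditions, Problems with previous anesthesia, Employment Status". No PostopQRS or cognitive result is among them.

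The primary test takes no covariates in either document. Protocol 2.7 has "Statistical analysis for the primary outcome will be with the Chi-squared test". SAP 6.2 has "A Fisher's Exact test was used to analyze the primary outcome of cognitive recovery at week 1 following laparoscopic surgery". SAP 6.4 reports no further analyses. Randomization is stratified by surgery type only (Protocol 2.7, SAP 3.2), so baseline cognition is balanced by chance alone.

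**The concern.** When a patient is scored against their own earlier result, that result is part of the endpoint. If it was high partly by luck, the week-1 target is harder to reach; if it was low partly by bad luck, the target is easier. This is regression to the mean. The protocol accepts that performance varies between tests, since that is the stated reason for the tolerance. The tolerance lowers the target for everyone but does not remove its dependence on the baseline result.

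Two things follow. A variable likely to predict the outcome, already collected before surgery, is left out of the analysis, so the estimate is less precise than it could be. And a reader who wants to know whether the arms started level on the variable that defines the endpoint cannot find out, although smoking and employment status are tabulated.

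**Working it through.** **Step 1. The plan's own figure.** Inputs from Protocol 2.7: 85% recovered in the better arm, a 15-point difference (so 70% in the other arm, which is derived and not stated), two-sided alpha 0.05, power 90%, 1:1 allocation, Chi-squared.

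n = [1.960 × √(2 × 0.775 × 0.225) + 1.282 × √(0.70 × 0.30 + 0.85 × 0.15)]² / 0.15² = (1.157 + 0.745)² / 0.0225 = 160.8, so 161 per group. The stated figure reproduces exactly.

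**Step 2. An illustrative model.** The documents give neither the tolerance nor the correlation r between baseline and week-1 cognition. Assume one standardized, normally distributed score on each occasion, with r from 0.5 to 0.9. Recovered means week-1 score ≥ baseline − c, where c is the net tolerance. The standard deviation of the change is √(2(1 − r)), so c = z(p) × √(2(1 − r)) gives overall recovery p.

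**Step 3. Dependence on baseline.** For a patient b SD from the mean baseline, P(recovered) = Φ[(c − (1 − r)b) / √(1 − r²)]. For r = 0.7 and p = 70%: c = 0.524 × 0.775 = 0.406 and √(1 − r²) = 0.714. At b = −1 this is Φ(0.706/0.714) = 84%; at b = +1 it is Φ(0.106/0.714) = 56%.

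| r | 70% arm at −1, 0, +1 SD | 85% arm at −1, 0, +1 SD |
|---|---|---|
| 0.5 | 88%, 73%, 51% | 96%, 88%, 73% |
| 0.7 | 84%, 72%, 56% | 94%, 87%, 76% |
| 0.9 | 78%, 71%, 62% | 90%, 86%, 80% |

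**Step 4. Chance imbalance.** With 161 per arm, the standard error of the difference in mean baseline is √(2/161) = 0.111 SD, so the 95% limit is 1.96 × 0.111 = 0.22 SD. With no treatment effect, an imbalance δ shifts the recovery difference by Φ[(c + (1 − r)δ/2)/√(2(1 − r))] − Φ[(c − (1 − r)δ/2)/√(2(1 − r))].

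| r | Shift at 0.22 SD, 70% recovered | Shift at 0.22 SD, 85% recovered |
|---|---|---|
| 0.5 | 3.8 points | 2.5 points |
| 0.7 | 2.9 points | 2.0 points |
| 0.9 | 1.7 points | 1.1 points |

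The range is therefore about 1 to 4 points at the 95% limit. At a one-standard-error imbalance (0.11 SD) it is 0.6 to 1.9 points. For comparison, the standard error of the recovery difference is √(0.3375/161) = 4.6 points, and the target is 15.

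**Step 5. Power and type I error.** There were 4,000 simulated trials per scenario at 161 per arm. The adjusted analysis was a risk difference standardized from a logistic model with treatment and baseline.

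| r | Power: Chi-squared | Power: Fisher | Power: adjusted | Null rejection: Chi-squared | Null rejection: Fisher | Null rejection: adjusted |
|---|---|---|---|---|---|---|
| 0.5 | 89.5% | 87.4% | 93.9% | 5.3% | 4.1% | 5.3% |
| 0.7 | 90.6% | 87.9% | 92.8% | 5.0% | 3.5% | 5.3% |
| 0.9 | 90.1% | 87.6% | 90.9% | 5.2% | 3.7% | 5.6% |

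Simulation error is about √(0.9 × 0.1/4000) = 0.5 points for power and √(0.05 × 0.95/4000) = 0.3 points for null rejection. The gain over Chi-squared is 4.4, 2.2 and 0.8 points, which is about 0 to 4 once simulation error is allowed for. Chi-squared exceeds Fisher by 2.2, 2.7 and 2.5 points with no covariate involved.

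**The case against.** The strongest reply is that nothing here is invalid. Randomization balances baseline cognition in expectation, and chance imbalance is ordinary sampling error that the unadjusted standard error already covers. The simulated null rejection rates bear this out: about 5% for Chi-squared and below that for Fisher. A reader might infer from the dependence on baseline that the comparison is biased. The documents do not support that, and this part of the reply stands in full.

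The power gain can also be made to look larger than it is. Setting Fisher (87.4% to 87.9%) against the adjusted analysis (90.9% to 93.9%) suggests 3 to 7 points, but 2 to 3 of those are Fisher's conservatism, which is a separate matter. Only the comparison with Chi-squared isolates the baseline score.

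A third tempting inference is that patients with very low baselines cannot fail, and so dilute the 15-point difference. That needs the size of the tolerance, the score range and the rule for combining tests into a domain result, and the documents give none of these. The planning rates are also said to come from earlier work with this scale, so any such patients may already be counted in the 85%.

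Finally, the protocol speaks of baseline values and describes no composite score, and the scale already uses a tolerance and parallel forms. This limits how literally the one-score model can be read. It does not explain why the baseline results are missing from the table.

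**Conclusion.** The point holds as a matter of precision and transparency. The endpoint is scored against a pre-operative result that the SAP neither shows by arm nor uses in the primary test. The unadjusted comparison remains valid, and the sample size of 161 per group is unaffected.

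The size is modest: a shift of about 1 to 4 points at the 95% limit of chance imbalance, and about 0 to 4 points of power over Chi-squared. These figures rest on a single normally distributed score, a correlation of 0.5 to 0.9, a tolerance set to match the planned rates, and 70% recovery inferred for the lower arm. None of the first three is in the documents. That the baseline predicts recovery, and in which direction, holds across the whole assumed range; its strength depends on r. No conclusion about floor effects or dilution can be drawn from what the documents give.

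**What to change.** 1. Add the baseline PostopQRS cognitive results by arm, with the number missing, to the SAP 5.5 table.
2. Pre-specify in SAP 6.2 a logistic model for week-1 cognitive recovery with treatment, baseline cognitive score and the surgery-type stratum. Report the adjusted risk difference with its 95% CI beside the unadjusted test. The SAP should state in what form the baseline cognitive results enter the model, since the documents do not describe how the domain is composed.
3. The SAP is written in the past tense. If allocation has already been revealed, label the adjusted estimate supportive and keep the planned test primary. The table row can be added at any stage.

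The data are already collected before surgery. The cost is SAP wording, one table entry, and one additional model and estimate to explain.
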